### Substudy 2: Patients with N1303K CFTR.

The primary analysis will be to estimate the mean absolute change in sweat chloride concentration from baseline through day 28 among the adolescents and adults with at least one copy of an N1303K mutation and a minimal function mutation who are not currently modulator eligible. A one-sided 0.025 alpha level single sample t-test comparing this estimate to no change will be reported, along with corresponding confidence intervals. A complementary analysis evaluating the percentage of participants with  $\geq 15$  mmol/L decline will also be reported. With a previously estimated 9.7 mmol/L standard deviation of the change in sweat chloride for successful modulator trials previously (Boyle et al., 2014; Vermeulen et al., 2017), an anticipated 6% of responders would be expected by chance alone. Therefore, the treatment response prevalence will be compared to a reference rate of 6%. For longitudinal sweat chloride through day 28 and for secondary endpoints (absolute change in ppFEV1, CFQ-R respiratory domain, and weight/BMI from baseline through day 28), means at each time point and changes over time will be summarized along with corresponding confidence intervals estimated by mixed effects models to account for within-subject correlation.

Changes in sweat chloride following treatment with ETI will be correlated with iPS cell responses in vitro, in addition to secondary clinical outcomes measures. A non-linear Spearman's correlation coefficient will be estimated for each measure paired with iPS cell responses in vitro, with corresponding fitted curves displayed graphically along with coordinates for participant's paired in vivo and in vitro responses. We expect variation both in sweat chloride and in iPS cell short circuit current measurements ( $I_{sc}$ ) due to heterogeneity in genotypic profiles among participants in the study. Sample selection for iPS cell experiments will be coordinated across studies to optimize power and unbiasedness as specified in a sample selection plan.

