**Human Subjects Involvement**

Procedures	Screening/ Enrollment Day -28 to -1	Baseline Visit 1, Day 1	Study Visit 2 (phone call) Day 7 +/-2 days	Study Visit 3 Day 14 +/-2 days	Study Visit 4 Day 28 +/-2 days	Final Study Visit Day 56 +/-2 days
Informed consent	X					
Medical history	X	X	X	X	X	X
Physical exam	X	X		X	X	X
Cutaneous punch biopsy and/or blood sample A		X				X E
CFTR genotype	X					
Spirometry	X	X		X	X	X
Oxygen saturation	X	X		X	X	X
Sweat chloride testing	X	X		X	X	X
Safety laboratory assessment B	X	X		X	X	X
Pregnancy Test C	X	X				X
EKG	X			X		
Ophthalmologic exam D	X					
Drug accountability		X		X	X	
Questionnaire (CFQ-R)	X	X		X	X	X
Administer study drug		X				X
Concomitant medication	X	X	X	X	X	X
Adverse event assessment		X	X	X	X	X

A Substudy 1: cutaneous punch biopsy. Substudy 2: blood sample with optional cutaneous punch biopsy.

B Renal and liver panels, CBC/Diff urinalysis

C Females of reproductive age

D Slit lamp ophthalmologic exam if not done within 3 months before screening for those ages 12-17 at the time of screening

E If necessary to produce additional iPS cells

Minor protocol changes for Substudy 2 are described in text.

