#### Sample Size

With a sample size of 20 participants, we anticipate 99% power to detect a mean sweat chloride decrease of 10 mmol/L assuming a standard deviation of 9.7 mmol/L (Boyle et al., 2014; Vermeulen et al., 2017) under a one-sided 0.025 alpha-level t-test. With a higher standard deviation of 15 mmol/L, the power decreases to 81% to detect a mean decrease of 10, but we retain 98.9% power to detect the hypothesized mean decrease of 15 mmol/L.

SAEs and AEs will be tabulated using standard coding terms sorted by System Organ Class (SOC). The incidence of AEs will be tabulated by seriousness and severity. The number of SAEs and AEs will be

summarized as follows: (i) The proportion of subjects with at least one (S)AE, (ii) The average number of (S)AEs per subject, and (iii) The rate of (S)AEs per subject week of follow-up.

**Expected Outcomes** Subjects will be recruited by study investigators as above, including through the CF Foundation Therapeutic Development Network resource. Please note that based on considerable past experience conducting clinical trials involving CF subjects at both participating institutions, we do not have concerns regarding our ability to perform the patient-oriented study described here, or to propagate and characterize iPS cells (Crane et al., 2015; Mou et al., 2015; Hawkins et al., 2017; Jacob et al., 2017). The protocol will furnish one test of our hypothesis that thresholds of CFTR activity in differentiated iPS cells encoding partial function mutations *in vitro* or *in vivo* predict benefit following Trikafta™ *in vivo*. If a strong correlation can be established between Trikafta™ response *in vitro* and *in vivo* (e.g., FEV1) in both substudies, the clinical results will provide early evidence for possible usefulness of *in vitro* surrogate models in this setting.

**Scientific Rigor** All *in vitro* and *in vivo* studies will be conducted with appropriate “n” so that therapeutically relevant conclusions can be drawn. Multiple biologic or technical replicates will be performed and evaluated in blinded fashion by an experienced statistician. CFTR mutations are equally prevalent in both sexes, and we expect iPS cells studied in human subjects carrying partial function mutations will reflect male and female individuals equally.

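### Substudy 2 could average its two untreated sweat chloride values as the baseline: a cheap precision gain, not an error in the plan

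*Combined protocol and SAP*

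**What the plan says.** Section 11, Substudy 2, sets the primary analysis as the "mean absolute change in sweat chloride concentration from baseline through day 28". It adds: "A one-sided 0.025 alpha level single sample t-test comparing this estimate to no change will be reported". It also compares the proportion of participants whose sweat chloride falls by at least 15 mmol/L with a 6% chance rate derived from an SD of change of 9.7 mmol/L, and it correlates the changes with iPS cell response. No sentence there defines baseline.

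In the schedule of events (Section 5), the row "Sweat chloride testing" is marked at Screening (Day -28 to -1), Day 1, Day 14, Day 28 and Day 56. The Day 1 column carries the baseline label and Screening is a separate column. The Day 1 description in Section 5 lists drug administration last, and Section 6 excludes approved modulator treatment in the previous 6 months. Both early values can therefore be read as untreated.

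Section 6 admits patients on sweat chloride below 80 mmol/L and/or pancreatic sufficiency, or on carrying N1303K. Substudy 2 patients do not need to meet the sweat chloride limit.

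The Substudy 2 Sample Size section states: "With a sample size of 20 participants, we anticipate 99% power to detect a mean sweat chloride decrease of 10 mmol/L". That figure uses the planning SD of 9.7. For a less favourable SD the section says: "With a higher standard deviation of 15 mmol/L, the power decreases to 81% to detect a mean decrease of 10". At that same SD it reports 98.9% power for the larger, hypothesized fall of 15 mmol/L.

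**The concern.** A change score carries the measurement error of its baseline in full. With two untreated values per patient and only one in use, the change is noisier than the data require. The extra noise widens the confidence interval for the primary mean, raises the number of patients who cross the 15 mmol/L line by chance, and weakens the correlation between sweat chloride change and iPS response. That correlation is central to the trial's purpose, and no power is given for it in Substudy 2.

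The usual reason for leaving a screening value out of the baseline is that patients were selected on it, which brings regression to the mean. For N1303K carriers the 80 mmol/L limit does not apply, so that reason is weak here. In Substudy 1 it does apply.

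**Working it through.** **Inputs from the documents:** n = 20; one-sample t-test, one-sided alpha 0.025; SD of change 9.7 or 15 mmol/L; decrease of 10 or 15 mmol/L; responder cut-off 15 mmol/L; chance rate 6%.

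**Inputs not in the documents (assumed):** the share f of the change variance that is within-patient visit error, 0 to 100%; the correlation ρ between Screening and Day 1 errors, 0 to 0.5.

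**Step 1. Reproduce the plan.** Power comes from the noncentral t distribution with 19 df, noncentrality δ√20/SD and critical value 2.093.
- Decrease 10, SD 9.7: noncentrality 4.61, power 99.2% (stated 99%).
- Decrease 10, SD 15: noncentrality 2.98, power 80.7% (stated 81%).
- Decrease 15, SD 15: noncentrality 4.47, power 98.9% (stated 98.9%).
- Chance of a fall of at least 15: Φ(−15/9.7) = 6.1% (stated 6%).

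All four figures reproduce.

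**Step 2. Effect of averaging.** Let V = SD². With one value before and one after treatment, each visit's error variance is s² = fV/2. Averaging two baseline values replaces s² by s²(1 + ρ)/2, so

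new variance = V − fV(1 − ρ)/4.

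At f = 100% and ρ = 0 this is 0.75V, a fall in SD of 13.4%. At f = 0 nothing changes.

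**Step 3. Results with ρ = 0, planning SD 9.7.** The half-width is 2.093 × SD/√20.

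| f | SD | 95% CI half-width | Power, decrease 10 | Chance rate Φ(−15/SD) |
|---|---|---|---|---|
| 0 | 9.70 | 4.54 | 99.2% | 6.1% |
| 25% | 9.39 | 4.40 | 99.5% | 5.5% |
| 50% | 9.07 | 4.25 | 99.7% | 4.9% |
| 75% | 8.74 | 4.09 | 99.8% | 4.3% |
| 100% | 8.40 | 3.93 | 99.9% | 3.7% |

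**Step 4. Results with ρ = 0, SD 15.**

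| f | SD | Power, decrease 10 | Power, decrease 15 |
|---|---|---|---|
| 0 | 15.00 | 80.7% | 98.9% |
| 25% | 14.52 | 83.2% | 99.2% |
| 50% | 14.03 | 85.6% | 99.5% |
| 75% | 13.52 | 88.0% | 99.7% |
| 100% | 12.99 | 90.4% | 99.8% |

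If only the 9.7 part of an SD of 15 is noise, the variance is 225 − 94.09/4 = 201.5, the SD is 14.19, and power for a decrease of 10 is 84.8%.

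**Step 5. Correlated errors.** With ρ = 0.5 the variance reduction is halved. At SD 15 and a decrease of 10, power is then 85.6% at f = 100% and 83.2% at f = 50%.

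**Step 6. Correlation with iPS response.** If visit error is unrelated to the iPS measurement, the covariance is unchanged and a product-moment correlation rises by the factor 1/√(1 − f/4): 1.03 at f = 25% and 1.07 at f = 50% (ρ = 0). The plan uses Spearman's coefficient, so this is a guide only.

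**Step 7. Drift.** If sweat chloride shifts systematically by D between Screening and Day 1, the averaged baseline differs from Day 1 by D/2, and so does the estimated mean change. A drift of 4 mmol/L moves it by 2. At SD 9.7 the best-case gain in half-width is 4.54 − 3.93 = 0.61, which a drift of about 1.2 mmol/L would match in bias.

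**The case against.** The strongest case against is that nothing here is wrong. Change from a Day 1 value taken before dosing is conventional, and the schedule labels that visit as baseline. A reader might infer that baseline is undefined or that the analysis cannot be run; the schedule does not support that.

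A reader might also take the 81% figure to mean that the substudy is short of power. That figure needs both an SD above the planning value and an effect below the hypothesized 15 mmol/L. The same sentence of the plan gives 98.9% at SD 15 for the hypothesized effect. Quoting only a rise to between 86% and 90% would be selective too, because it needs a noise share of at least 50% and independent errors.

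The plan expects real differences between patients from genotype, which averaging does not remove. At f = 100% there would be no true variation in response for iPS cells to predict, so the 90% power figure and a better iPS correlation cannot both be claimed.

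Nor is the change free. The 6% reference equals Φ(−15/9.7) and would no longer match. Screening may be up to 28 days before dosing, so the drift in Step 7 is possible in a single-arm comparison with zero. Section 6 requires clinical stability before both Screening and Day 1, which limits drift but does not exclude it. Selection is not wholly absent either: the diagnostic footnote in Section 6 lists sweat chloride of at least 60 mmol/L as one route, with two disease-causing mutations as an alternative.

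All of this stands. It reduces the point to an optional improvement but does not remove it.

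**Conclusion.** This is a cheap improvement. The plan's power figures and its chance rate are correct as stated. Its weight lies in interval width, the individual responder classification and the iPS correlation more than in the power of the primary test, where only the SD 15, decrease 10 scenario shows a gain of more than about one point.

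The ranges rest on an assumed noise share and error correlation, equal error variance at each visit, and a single post-treatment value. The plan's wording leaves open whether Day 14 also enters. If 9.7 already described a change to the mean of Days 14 and 28, and all of it were noise, then s² = 94.09/1.5 = 62.7. The averaged baseline would then give an SD of 7.92 and a chance rate of 2.9%.

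**What to change.** Before data are examined, add to Section 11, Substudy 2:

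- Baseline sweat chloride is the mean of the Screening and pre-dose Day 1 values, for the primary change, the responder rate (decline of at least 15 mmol/L) and the iPS correlation.
- Day 1 alone is a sensitivity analysis for the same three results, which would also expose drift.
- The 6% reference is recalculated for the averaged baseline, with the assumed noise share stated: about 3.7% to 5.5% at SD 9.7 for f from 100% to 25% with independent errors. Leaving it at 6% would make the comparison conservative.

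Keep Day 1 as baseline in Substudy 1, where the Screening value can decide eligibility.

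The cost is a few sentences and one recalculated rate, with no new visit or sample. The downsides are the possible D/2 shift, a baseline definition that differs between substudies, and the re-derived reference. If the sponsor prefers Day 1, a sentence saying so would still close a choice that could otherwise be made after seeing the data.

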#### 6. Participant selection:

##### Inclusion Criteria:

- Provision of signed and dated informed consent form, and when appropriate, assent form
- Stated willingness to comply with all study procedures and availability for the duration of the study
- Male or Female age ≥12
- A clinical diagnosis of CF or CFTR-related disease\* and either: 1) evidence for a partial function mutation not currently covered or likely to be covered for FDA treatment with a CFTR modulator (Substudy 1), or 2) N1303K CFTR and a minimal function mutation (Substudy 2).
- Sweat Chloride < 80 mmol/L and/or pancreatic sufficiency (no exogenous pancreatic enzyme supplement therapy) or carrying the N1303K CFTR variant

- Able to perform spirometry meeting ATS criteria for acceptability and repeatability
- Clinically stable in the past 4 weeks with no evidence of CF exacerbation (prior to Screening AND Day 1)
- Willingness to use at least one form of acceptable birth control including abstinence or condom with spermicide. This will include birth control for at least one month prior to screening and agreement to use such a method during study participation for an additional four weeks after the last administration of study drug.
- Ability to take Trikafta™.
- Agreement to adhere to all current medical therapies as designated by the CF care center physician.

\* A diagnosis of CF as defined by current guidelines: one or more clinical features consistent with the CF phenotype or positive CF newborn screen AND one or more of the following criteria: sweat chloride  $\geq 60$  mmol/L by quantitative pilocarpine iontophoresis or 2 well characterized disease-causing CFTR gene mutations

OR

With the consensus of two study co-investigator physicians, a clinical diagnosis of CF or CFTR-related disorder with documented evidence of chronic pulmonary disease (chronic cough with sputum production, persistent pulmonary radiographic abnormalities (e.g bronchiectasis), chronic abnormality in ppFEV1, and/or persistent colonization with a typical CF pathogen)

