All analyses will be conducted using the intention to treat principal, where all subjects will be included in analysis regardless of how long they took the study medication. Statistical significance will be assessed at the 0.05 level and analyses conducted using SAS v. 9.4 (SAS Institute; Cary, NC).

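### Is the 6% chance rate for sweat chloride responders in Substudy 2 unsound because its SD comes from successful modulator trials and is not checked against off-drug readings?

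*Combined protocol and SAP*

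**What the plan says.** The text is in section 11, Statistical Methods, under Substudy 2. The primary analysis is a one-sample t-test, one-sided at 0.025, of the mean change in sweat chloride from baseline through Day 28, reported with confidence intervals. The responder share is introduced separately: "A complementary analysis evaluating the percentage of participants with" a fall of 15 mmol/L or more. The plan takes 9.7 mmol/L as the "standard deviation of the change in sweat chloride for successful modulator trials previously", citing two published studies, and derives from it that 6% of responders "would be expected by chance alone". It then fixes the comparator: "Therefore, the treatment response prevalence will be compared to a reference rate of 6" percent. It names no test, alpha level, sidedness or success rule for this comparison.

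The Substudy 2 Sample Size section uses 9.7 as the base case and then varies it: "With a higher standard deviation of 15 mmol/L, the power decreases to 81" percent for a mean decrease of 10 mmol/L. It states a hypothesized mean decrease of 15 mmol/L.

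In the schedule of events in section 5, the row "Sweat chloride testing" is marked at both Screening and Day 1. The sweat chloride limit in the Inclusion Criteria has an alternative, "or carrying the N1303K CFTR variant", so that limit does not select Substudy 2 participants on their Screening value.

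**The concern.** A chance rate should rest on how much sweat chloride varies when no drug is acting. The plan's SD is described as coming from trials in which the drug worked. An SD of change among treated patients can include real differences in response as well as measurement and day-to-day variation, so it need not be the SD under no effect. These participants might also vary more than those in the cited trials.

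With no control arm, 6% is the only benchmark the plan gives for the responder share. If the true chance rate were higher, an inert drug could look active; if it were lower, a real effect could be missed. Two off-drug readings, Screening and Day 1, are already scheduled, and the plan does not use them to check the figure. The Sample Size section allows an SD of 15 for power, yet the 6% is not revisited there.

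**Working it through.** **Inputs.** From section 11, Substudy 2: SD of change 9.7 mmol/L, responder threshold 15 mmol/L, reference rate 6%. From its Sample Size section: n = 20, alternative SD 15, hypothesized mean decrease 15. Assumptions, not in the documents: normal changes, an exact binomial test at one-sided 0.025, and off-drug SDs of 8 and 12 as a range.

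**1. The plan's figures reproduce.** With mean change zero, P(decline ≥ 15) = Φ(−15/9.7) = Φ(−1.546) = 6.1%, against 6% stated. Power from the noncentral t with n = 20:

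| Mean decrease | SD | Recomputed | Stated |
|---|---|---|---|
| 10 | 9.7 | 99.2% | 99% |
| 10 | 15 | 80.7% | 81% |
| 15 | 15 | 98.9% | 98.9% |

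**2. What a different off-drug SD would do.** For X ~ Bin(20, 0.06), P(X ≥ 4) = 0.029 and P(X ≥ 5) = 0.0056, so the assumed test needs 5 responders. The chance that an inert drug reaches 5 is:

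| Off-drug SD | Chance rate Φ(−15/SD) | P(X ≥ 5) |
|---|---|---|
| 8 | 3.0% | 0.03% |
| 9.7 | 6.1% | 0.6% |
| 11.0 | 8.7% | 2.5% |
| 12 | 10.6% | 5.3% |

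At the plan's own SD the error rate is well below 2.5%, and the level holds up to an SD of about 11.0. If 9.7 contains variation in response, the off-drug SD is smaller and the true position lies higher in this table, where the test is stricter than it needs to be. If one-sided 0.05 were assumed instead, the cut would be 4, with an error of 3.1% at SD 9.7 and the level holding up to about 10.2.

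**3. Effect at the planned treatment effect.** With a mean decrease of 15, the threshold equals the mean, so the expected responder share is 50%, or 10 of 20. Against a reference of 16%, about the rate implied by an SD of 15 (Φ(−1) = 15.9%), 10 of 20 has a one-sided p of 0.0004. That reference would need 8 responders, and with a 50% share P(X ≥ 8) = 87%. The choice of reference matters mainly for smaller effects: 5 of 20 has p = 0.006 against 6% and 0.043 against 10%.

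**4. Could the off-drug readings check the 6%?** Suppose the SD of the 20 Screening-to-Day 1 changes came out at exactly 9.7. The chi-square interval on 19 degrees of freedom is

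9.7 × √(19/χ²) = 7.4 to 14.2,

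which gives chance rates from Φ(−15/7.4) ≈ 2% to Φ(−15/14.2) ≈ 14%. Counting off-drug decliners is coarser still: 0 of 20 has an exact 95% interval of 0 to 16.8%. A result that agreed perfectly with 6% would therefore not exclude 3% or 10.6%. Screening falls anywhere from Day −28 to Day −1, so the off-drug interval does not match the four weeks on treatment.

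**The case for a change.** The best argument for the concern is that the plan presents 6% as what chance alone would produce while naming a source that need not measure chance. The documents give no figure identified as an off-drug SD, the readings are already scheduled, and a supportive analysis would cost a few sentences. Counts such as 3 or 5 of 20 would read differently against 3%, 6% and 10%: 3 of 20 has p = 0.115 against 6% but 0.021 against 3%.

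Part of this stands. The 6% is an assumption about variation without drug, and the documents cannot verify it. The plan also leaves the test and its level unnamed for this comparison, which is a missing detail and not a wrong choice. But the plan names the trials, not the arm, so the documents do not show that 9.7 comes from treated patients. The possible error runs in both directions. The false-positive rates require a test, a level and off-drug SDs that the plan does not contain, applied to a result that triggers no decision. The supportive analysis would leave 6% in place and could not settle whether it is right.

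**Conclusion.** There is no error in the plan on this point. The 6% follows from its stated input (6.1%). It is cautious if that input includes variation in drug response, and under the assumed one-sided 0.025 test it keeps its level up to an off-drug SD of about 11.0. At an assumed SD of 12 the error would reach 5.3%, in a complementary comparison with no success rule attached. The primary t-test does not use the 6% and takes its variance from the observed data. At the hypothesized mean decrease of 15 mmol/L, the expected 10 of 20 responders exceeds every reference from 2% to 16% by a wide margin.

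A Screening-to-Day 1 analysis is an optional addition and its absence is not a flaw. This conclusion assumes normally distributed changes, no mean drift without drug, and an exact binomial test where the plan names none. Whether 9.7 came from treated, control or pooled participants cannot be settled from the documents.

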The study is an open-label clinical trial of orally-administered Trikafta™ in subjects with CF and carrying certain mutations that are without FDA approved modulator treatment. Subjects will be given the study drug elexacaftor 100 mg/tezacaftor 50 mg/ivacaftor 75 mg (2 pills once daily in the morning) and ivacaftor (150 mg) once daily in the evening, as the FDA-registered agent, Trikafta™. Dose and schedule will be identical to what has already been FDA-approved for the F508del CF genotype. Enrollment is planned at two centers, Emory University and University of Alabama at Birmingham. In Substudy 1, patients with residual CFTR function (based on sweat chloride < 80 meq/L or pancreatic sufficiency) will be tested. In Substudy 2, patients with CF encoding the N1303K variant will be enrolled as a “case in point” – emblematic of variants with *in vitro* evidence of Trikafta™ responsiveness who are not approved (i.e., not “on label” for the drug). iPSC-derived airway epithelial monolayers from these patients will be examined for their ability to predict FEV1 and sweat chloride response and other clinical endpoints. Our study will not significantly increase the risks (or decrease the acceptability of risks) associated with the use of Trikafta™ in CF.

Human subject participation will consist of a screening day (-28), day 1 (+/-2), day 7 (+/- 2) [phone call visit], day 14(+/-2), day 28 (+1/- 2) and day 56 (+/-2) follow up (wash-out). The visits will include patient history with concomitant medication review, physical exam, safety laboratory assessments (renal and liver panels, CBC/Diff, urinalysis), serum and urine pregnancy testing, CFTR genotype, spirometry, O2 saturation, sweat chloride test, ophthalmology exam in children, cutaneous punch biopsy and/or blood sample for iPSC derivation, EKG, drug accountability and questionnaire (CFQ-R assessment), and adverse event assessment.

We anticipate the screening and enrollment visit will require 4-6 hours to complete the informed consent, medical history, O2 saturation, concomitant medication review, physical exam, safety laboratory assessments (CBC/Diff, RENAL/LFT chemistry panel, and urinalysis), EKG, CFTR genotyping, questionnaire, serum pregnancy test for females, sweat chloride test, and spirometry.

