#### Sources of Patient-Derived Material

- Review of patient medical records and demographic information
- History and physical exam
- Blood and urine for safety studies (<6 tablespoons (depending on weight) of blood per visit)
- Sweat chloride results
- Questionnaire data
- Spirometry (FEV1, FVC, and FEF25-75%) calculated per Hankinson equation
- Cutaneous punch biopsy (3 mm) and/or blood sample /iPS cell derivation
- O2 saturation
- EKG
- Ophthalmologic exam
- CFTR genotype
- Pregnancy test
- Drug accountability

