For other outcomes of interest including sweat chloride levels, quality of life, and weight/BMI, we will apply a mixed effect model to examine the change in these measures over the study duration. Models will include a subject-specific intercept, to account for variability among subjects prior to the start of the treatment, and a categorical variable for time (baseline, day 14, day 28, day 56). A Dunnet's post-hoc comparisons procedure will be used to determine which time points demonstrated a significant change from baseline. Using the same mixed effects models, we will include  $\Delta Isc$  as predictors of *in vivo* improvement. We will also test the interaction between time and  $\Delta Isc$  to determine when *in-vitro* response is most associated with change in clinical response. Adverse events and other safety endpoints will be tabulated and reported using counts and percentages or means and standard deviations, as appropriate.

In addition, because clinical parameters may vary among patients prior to the start of therapy, we will also approach the analysis using a modified N of 1 design configured for the purpose of comparing iPS studies in contrast to the aggregate analysis described above. Using the framework of single subject research, we will evaluate therapeutic response in individual subjects by an interrupted time series (ITS) approach. Briefly, in the absence of an independent control group, ITS analysis is a quasi-experimental design in which each subject acts as their own control and is followed serially in time prior to and after an interruption (in this case, the start of treatment). If the treatment has causal

impact, the post-intervention time series will have a different level or slope than the pre-intervention series. Time series models also have the power to test and correct for possible cyclical patterns and outliers. Using segmented regression analysis, we will conduct ITS models for each of the subjects enrolled in the trial. A significant change in slope from the pre-treatment period will indicate a significant treatment effect. ITS models will be constructed for each outcome of interest where historical and pre-treatment data are available. The change in slope will also be correlated with the *in-vitro* response using Spearman's rank-order correlation coefficient.

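### Weight/BMI change is analysed unstandardised and without a control in a pooled group from age 12, so mean weight gain includes some normal adolescent growth

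*Combined protocol and SAP*

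**What the plan says.** - **Population.** The inclusion criteria in Section 6 admit "Male or Female age ≥12", with no upper limit. The Substudy 2 part of Section 11 defines its primary analysis "among the adolescents and adults with at least one copy of an N1303K mutation" plus a minimal function mutation, as one group. The expected share of adolescents is not given.
- **Design.** Section 5 states: "The study is an open-label clinical trial of orally-administered Trikafta™ in subjects with CF". Section 11 describes its time-series method as suited to use "in the absence of an independent control group, ITS analysis is a quasi-experimental design in which each subject acts as their own control".
- **Role of weight.** Section 4 lists weight gain among the secondary endpoints, with a secondary objective of verifying safety and establishing efficacy. Substudy 2 takes over the same list, except that sweat chloride becomes primary.
- **Substudy 2 analysis.** The secondary endpoints are "absolute change in ppFEV1, CFQ-R respiratory domain, and weight/BMI from baseline through day 28". Means and changes are to be "summarized along with corresponding confidence intervals estimated by mixed effects models to account for within-subject correlation".
- **Substudy 1 analysis.** "For other outcomes of interest including sweat chloride levels, quality of life, and weight/BMI, we will apply a mixed effect model". That model has a subject intercept and categorical time (baseline, days 14, 28 and 56). Dunnett comparisons identify the visits that differ significantly from baseline.
- **Contrast.** The list of data sources in Section 5 has spirometry "calculated per Hankinson equation", so lung function is expressed against a reference population. No z-score, percentile, age term or separate adolescent summary is named for weight or BMI.

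**The concern.** In a participant who is still growing, the expected weight change over four weeks without any drug is above zero. With one arm and no standardisation, the pooled mean change estimates the drug effect plus the growth of the adolescents in the sample. The direction of the error is fixed and favours the drug. Its size depends on an age mix that the plan does not state.

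Two analyses are affected. In Substudy 2 the day 28 estimate and its confidence interval are shifted upward. In Substudy 1 the same shift enters each Dunnett comparison with baseline, including day 56, about four weeks after dosing ends. What is at stake is the reading of a secondary efficacy endpoint: part of a reported weight gain could be growth.

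There is a smaller effect on the iPS question. Both substudies relate weight change to the in vitro response (ΔIsc in Substudy 1, iPS cell response in Substudy 2). Growth that differs by age adds variation to weight change unrelated to the drug.

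**Working it through.** **The plan's own figures.** The documents give no figure for weight or BMI. The only sizing figures for Substudy 2 concern sweat chloride (N = 20, one-sample t-test, one-sided 0.025). They reproduce with the noncentral t on 19 degrees of freedom: 99.2%, 80.7% and 98.9%, against the stated 99%, 81% and 98.9%. They do not involve weight and do not change.

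**Inputs from the documents.** N = 22 (Substudy 1) and N = 20 (Substudy 2); visits at days 28 and 56; three Dunnett comparisons with baseline; significance level 0.05.

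**Assumed inputs (not in the documents).** Adolescent share 25% to 50%; growth 0.2 to 0.5 kg per 4 weeks; SD of 4-week weight change 1.0 to 1.5 kg.

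**Step 1: shift in mean weight.** Shift = share × growth.
- Day 28, low: 0.25 × 0.2 = 0.05 kg. High: 0.50 × 0.5 = 0.25 kg.
- Day 56, if growth is steady: 0.10 to 0.50 kg.

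As a cross-check from annual growth of 3 to 7 kg (also assumed), 28/365.25 of a year gives 0.23 to 0.54 kg per adolescent. The same shares then give 0.06 to 0.27 kg at day 28.

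**Step 2: BMI.** Assume a gain of 0.3 to 1.0 kg/m² per year. Over 28 days that is 0.023 to 0.077 kg/m² per adolescent, and 0.006 to 0.04 kg/m² in the pooled mean. At day 56 it is 0.01 to 0.08 kg/m².

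**Step 3: Substudy 2 interval at day 28.** SE = SD/√20, that is 0.335 kg (SD 1.5) or 0.224 kg (SD 1.0). Shift/SE runs from 0.05/0.335 = 0.15 to 0.25/0.224 = 1.12. Treating the mixed-model interval as a one-sample t interval, the chance that a 95% interval excludes zero with no drug effect is 5.2% at the low end and 18.6% at the high end. At mid-range (37.5%, 0.35 kg, SD 1.25) it is 7.3%.

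**Step 4: Substudy 1 Dunnett comparisons.** SE = SD/√22, that is 0.320 or 0.213 kg. Shift/SE at day 28 runs from 0.16 to 1.17. For three comparisons with a shared baseline, the simulated two-sided critical value is about 2.41. The rate is P(|N(shift/SE, 1)| > 2.41), which is 1.6% per comparison when there is no drift.

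| Inputs (share, growth, SD) | Day 28 shift | Per-comparison rate, day 28 | Per-comparison rate, day 56 |
|---|---|---|---|
| 25%, 0.2 kg, 1.5 kg | 0.05 kg | 1.7% | 2.1% |
| 37.5%, 0.35 kg, 1.25 kg | 0.13 kg | 2.9% | 7.7% |
| 50%, 0.5 kg, 1.0 kg | 0.25 kg | 10.8% | 47% |

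The day 56 column doubles the drift and leaves the SD unchanged. A larger SD over eight weeks would lower it.

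**Step 5: a mostly adult sample.** With a 10% adolescent share, N = 20, SD 1.0 kg and 7 kg per year, an unadjusted two-sided 0.05 t-test at day 28 rejects 5.6% of the time. The problem is then negligible.

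**The case against.** The strongest reply is that little turns on this. Weight is not a primary endpoint in either substudy, no stopping rule uses it, and Section 11 says the study is not meant for FDA submission or label expansion. That stands, and it limits the point to a refinement.

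Second, the Substudy 1 interrupted time series compares each subject with their own pre-treatment slope, which absorbs steady growth. This stands in part. It is planned only where historical and pre-treatment data exist, it does not correct the aggregate mixed model, and Substudy 2 has no counterpart.

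A reader might also infer more than the documents support:

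- **That eight weeks of growth are counted as a drug effect throughout.** The Substudy 2 endpoint stops at day 28. Only the Substudy 1 model reaches day 56, which is off drug. A gain that continues at the same rate after dosing stops would itself point to a non-drug trend.
- **That the false-positive rate rises to 5.3% to 22%.** That range comes from an unadjusted 1.96 cut-off with N = 22. Substudy 2 plans estimates with intervals for weight, not a named test, and Substudy 1 uses Dunnett comparisons. On the same inputs these give 1.7% to 10.8% per comparison at day 28.
- **That age confounds the link between weight change and ΔIsc.** This needs age to be associated with ΔIsc as well. The documents show no such association, and the Substudy 2 text attributes variation in Isc to genotype. Without it, growth only adds noise.

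**Conclusion.** The point holds as a modest, directional bias in one secondary endpoint. Pooled raw weight change in an uncontrolled sample from age 12 includes growth, and nothing in the aggregate analyses of either substudy removes it. The shift is about 0.05 to 0.25 kg at day 28 and about twice that at day 56 in Substudy 1. These sizes rest wholly on the assumed adolescent share and growth rate, and the error rates also rest on the assumed SD. The direction needs only that some enrolled participants are still growing.

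For BMI the drift over four weeks is very small. The effect on the correlation with ΔIsc is noise, and becomes confounding only if age and ΔIsc happen to be associated in the sample. The primary endpoints, sample sizes and stated power are unaffected.

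**What to change.** In the Substudy 1 and Substudy 2 parts of Section 11:

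1. Add weight-for-age and BMI-for-age z-scores for participants under 20, using exact age at each visit, as a separate model. Z-scores and kilograms are in different units and cannot be two strata of one model.
2. Report raw weight and BMI change separately for adults.
3. Base any statement about drug-related weight gain on these two analyses. Keep the pooled raw change and label it descriptive.
4. Use z-score change when relating weight to ΔIsc in those under 20.

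The cost is SAP wording and a reference-table lookup from age, sex, height and weight, which BMI and percent-predicted FEV1 already require. The schedule of events has no separate row for height and weight, so confirm that both are recorded at each in-person visit. The downside is two reporting scales and small subgroups. At a 25% to 50% share, about 5 to 11 participants per substudy would be under 20, so intervals will be wider.
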